3.2 Target Indication and Pharmacologic Activity

VERU-111 is orally bioavailable bis-indole that binds the "colchicine binding site" of α and β tubulin and inhibits tubulin polymerization at low nanomolar concentrations. VERU-111 is neither a substrate for MDRs including P-gp, MRPs, and BCRP, nor CYP3A4. VERU-111 also decreases the transcription of β I, β III, and β IV-tubulin isoforms (Li 2012). VERU-111 was initially developed as an antiproliferative agent to treat malignancy. In preclinical animal models and confirmed in a Phase 1b/2 study in 39 men with metastatic prostate cancer, VERU-111 has a good safety profile as it does not cause neutropenia or myelosuppression and is well tolerated (clinical data on file at Veru Inc., Li 2012; Chen 2012). The Phase 1b study is ongoing with some men being treated with high daily doses of VERU-111 for greater than a year. *In vivo*, VERU-111 disrupts the microtubule filaments similar to nocodazole and colchicine, the central mechanism that contributes to both their antiviral and anti-inflammatory activities.

3.3 Study Rationale

Based on VERU-111's mechanistic similarities to other microtubular depolymerizing agents as well as its preclinical and clinical experience, VERU-111 could have a two-pronged approach to the treatment of SARS-CoV-2 (COVID-19) virus infection and the debilitating and sometimes lethal respiratory effects of the virus.

- 1. As an antiviral, it would have direct effects on S protein-microtubule trafficking with the potential to reduce the production of infectious virions particularly affecting viral replication and assembly and virion egress.
- 2. As an anti-inflammatory agent, it may reduce virally induced severe inflammation in the respiratory system and reduce the incidence of cytokine storm and septic shock that can occur in subjects that progress.

VERU-111 appears to be an appropriate candidate to enter clinical development for the treatment of SARS-CoV-2 (COVID-19) infection. In the absence of an effective treatment and the progression of the ongoing global pandemic and potentially future similar viral epidemic infections, Veru is initiating a Phase 2 clinical development program of VERU-111 for the treatment of SARS-CoV-2 infection (COVID-19).

4.0 STUDY OBJECTIVES

4.1 Primary Objectives

To demonstrate the efficacy of VERU-111 in the treatment of SARS-CoV-2 infection by assessing its effect on the proportion of subjects that are alive without respiratory failure at Day 29. Respiratory failure is defined as endotracheal intubation and mechanical ventilation, extracorporeal membrane oxygenation, high-flow nasal cannula oxygen delivery, noninvasive positive pressure ventilation, clinical diagnosis of respiratory failure with initiation of none of these measures only when clinical decision making is driven solely by resource limitation.

4.2 Secondary Objectives

The secondary objectives/endpoints on this study are:

Patient State	Descriptor	Score
Uninfected	No clinical or virological evidence of infection	0
Ambulatory	No limitation of activities	1
	Limitation of activities	2
Hospitalized, Mild disease	Hospitalized, no oxygen therapy	3
	Oxygen by mask or nasal prongs	4
Hospitalized, Severe disease	Non-invasive ventilation or high- flow oxygen	5
	Intubation and mechanical ventilation	6
	Ventilation + additional organ support – pressors, RRT, ECMO	7
Death	Death	8

1. WHO Ordinal Scale for Clinical Improvement (8-point ordinal scale) at Day 15, Day 22, and Day 29

a. Change in mean WHO Ordinal Scale for Clinical Improvement at Day 15

- b. Proportion of subjects that progress to Grade 5, 6, 7, or 8 on the WHO Ordinal Scale for Clinical Improvement at Day 15
- c. Proportion of subjects that progress to Grade 5, 6, 7, or 8 on the WHO Ordinal Scale for Clinical Improvement at Day 22
- d. Proportion of subjects that progress to Grade 5, 6, 7, or 8 on the WHO Ordinal Scale for Clinical Improvement at Day 29

- e. Change in mean WHO Ordinal Scale for Clinical Improvement at Day 22
- f. Change in mean WHO Ordinal Scale for Clinical Improvement at Day 29
- 2. Proportion of subjects with normalization of fever and oxygen saturation through Day 15, Day 22, and Day 29
- 3. Days on mechanical ventilation
- 4. Percentage of subjects discharged from hospital by Day 15 (and Day 22)
- 5. All-cause mortality at Day 15, Day 22, and Day 29
- 6. Proportion of patients alive and free of respiratory failure at Day 15, and Day 22
- Proportion of patients alive and discharged from the ICU at Day 15, Day 22, and Day 29
- Proportion of patients alive and discharged from hospital at Day 15, Day 22, and Day 29
- 9. Days in ICU
- 10. Days in hospital
- 11. Proportion of subjects on mechanical ventilation at Day 15, Day 22, and Day 29
- 12. Assess the pharmacokinetics of VERU-111 on Day 15
- 13. Assess the effect of VERU-111 on C-reactive protein from baseline to Day 9

4.3 Safety Objective

To assess the safety and tolerability of VERU-111

5.0 STUDY DESIGN

5.1 Treatment Groups and Allocation of Subjects

This randomized, placebo-control clinical study consists of two treatment arms: VERU-111 18 mg treated group, and Placebo treated group. Subjects will be randomized in a 1:1 fashion to the VERU-111 treated group and Placebo treated group, respectively.

All patients will receive standard of care for the treatment of SARS-CoV-2 infection (COVID-19).

5.2 Study Duration

The study will require that each subject in the VERU-111 treated groups receive 18 mg daily oral dose of VERU-111 or placebo for up to 21 days (Day 21) with final on study efficacy assessments done on Day 29 with safety assessments continuing to Day 60 of the study. The total duration of the study for a subject in the study from screening to follow-up visit (approximately Day 60 on study) will be approximately 62 days.

5.3 Efficacy Endpoints

5.3.1 Primary Endpoint

The primary endpoint for the study is the proportion of subjects that are alive without respiratory failure at Day 29. Respiratory failure is defined as endotracheal intubation and mechanical ventilation, extracorporeal membrane oxygenation, high-flow nasal cannula oxygen delivery, noninvasive positive pressure ventilation, clinical diagnosis of respiratory failure with initiation of none of these measures only when clinical decision making is driven solely by resource limitation.

5.3.2 Secondary Endpoints

The secondary endpoints on this study are:

Patient State	Descriptor	Score
Uninfected	No clinical or virological evidence of infection	0
Ambulatory	No limitation of activities	1
	Limitation of activities	2
Hospitalized, Mild disease	Hospitalized, no oxygen therapy	3
	Oxygen by mask or nasal prongs	4
Hospitalized, Severe disease	Non-invasive ventilation or high- flow oxygen	5
	Intubation and mechanical ventilation	6
	Ventilation + additional organ support – pressors, RRT, ECMO	7
Death	Death	8

1. WHO Ordinal Scale for Clinical Improvement (8-point ordinal scale)

- 1. Proportion of subjects that are Grade 5, 6, 7, or 8 on the WHO Ordinal Scale for Clinical Improvement at Day 15
- 2. Proportion of subjects that progress to Grade 5, 6, 7, or 8 on the WHO Ordinal Scale for Clinical Improvement at Day 22
- 3. Proportion of subjects that are Grade 5, 6, 7, or 8 on the WHO Ordinal Scale for Clinical Improvement at Day 29
- 4. Change in mean WHO Ordinal Scale for Clinical Improvement at Day 15.
- 5. Change in mean WHO Ordinal Scale for Clinical Improvement at Day 22
- 6. Change in mean WHO Ordinal Scale for Clinical Improvement at Day 29

- Proportion of subjects with normalization of fever and oxygen saturation through Day 15. This will be a composite of fever normalization maintained for at least 24 hours AND peripheral capillary oxygen saturation (SpO₂) >94% sustained for 24 hours.
- Proportion of subjects with normalization of fever and oxygen saturation through Day 22. This will be a composite of fever normalization maintained for at least 24 hours AND peripheral capillary oxygen saturation (SpO₂) >94% sustained for 24 hours.
- Proportion of subjects with normalization of fever and oxygen saturation through Day 29. This will be a composite of fever normalization maintained for at least 24 hours AND peripheral capillary oxygen saturation (SpO₂) >94% sustained for 24 hours.
- 10. Days on mechanical ventilation
- 11. All-cause mortality at Day 15
- 12. All-cause mortality at Day 22
- 13. All-cause mortality at Day 29
- 14. Proportion of patients alive and free of respiratory failure at Day 15
- 15. Proportion of patients alive and free of respiratory failure at Day 22
- 16. Proportion of patients alive and discharged from the ICU at Day 15
- 17. Proportion of patients alive and discharged from the ICU at Day 29
- 18. Proportion of patients alive and discharged from hospital at Day 15
- 19. Proportion of patients alive and discharged from hospital at Day 22
- 20. Proportion of patients alive and discharged from hospital at Day 29
- 21. Days in ICU
- 22. Days in hospital
- 23. Proportion of subjects on mechanical ventilation at Day 15
- 24. Proportion of subjects on mechanical ventilation at Day 22
- 25. Proportion of subjects on mechanical ventilation at Day 29
- 26. Pharmacokinetics of VERU-111 on Day 15
- 27. Change in mean C-reactive protein from baseline to Day 9.

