# 6.12.1 Primary Endpoint

QMD Ref: Worldwide-TMP-ST-005-7.0 Effective: 12Aug2019 Governing QMD: Worldwide-SOP-ST-		
Confidentiality Statement		
This document is the property of Worldwide Clinical Trials Inc. and may not be duplicated, copied, altered or removed from company without prior approval from Worldwide Quality Assurance or in compliance with Worldwide Standard Operating Procedures.		

REF: Worldwide-TMP-QA-001f-1.3

Worldwide Clinical Trials Controlled Quality Management Document		
WORLDWIDE CLINICAL TRIALS	Sponsor:	Veru Inc.
	Protocol Number:	V0211901
STATISTICAL ANALYSIS PLAN. PHASE 2-3-4		

The primary endpoint for the study is the proportion of subjects that are alive without respiratory failure at Day 29. Respiratory failure is defined as endotracheal intubation and mechanical ventilation, extracorporeal membrane oxygenation, high-flow nasal cannula oxygen delivery, noninvasive positive pressure ventilation, clinical diagnosis of respiratory failure with initiation of none of these measures only when clinical decision making is driven solely by resource limitation.

This analysis will compare the percentage of subjects that are alive without respiratory failure on Day 29 (responder).

Responders are subjects who have Grade 0-4 on the WHO Ordinal Scale for Clinical Improvement on Day 29. If subject was discharged from the hospital prior to Day 29 and WHO Ordinal Scale for Clinical Improvement is not collected at Day 29 then the last available observation before or at the time of discharge will be carried forward.

Non-responders are subjects who died before Day 29 or has Grade 5, 6, 7, or 8 on the WHO Ordinal Scale for Clinical Improvement on Day 29.

The number and percentage of responders will be summarized by treatment group. Responders will be analyzed using a logistic regression model. This model will include treatment as a factor, and study site, remdesivir use (No/Yes), dexamethasone use (No/Yes) and WHO Ordinal Scale for Clinical Improvement at baseline as a covariates. Odds ratios, standard errors, 95% confidence intervals and p-values for the treatment difference will be presented.

The primary analysis will be performed on the ITT population. A sensitivity analysis will be performed repeating the analysis on the EE population.

Example SAS code for the analysis is as follows:

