#### 6.12.2.4 Days on mechanical ventilation

Mechanical ventilation is defined as subject having 'Intubation and mechanical ventilation' or 'Ventilation + additional organ support – pressors, RRT, ECMO'.

'Days on mechanical ventilation' will be summarized using descriptive statistics (n, mean, standard deviation, median, minimum and maximum) by treatment group.

'Days on mechanical ventilation' will be the number of days on mechanical ventilation up to Day 29. If subject dies early in the study and was on mechanical ventilation at the time of the death then it is assumed that subject was on mechanical ventilation up to Day 29. A sensitivity analysis will be performed assigning the worst possible endpoint score for deaths (i.e., considered to be on mechanical ventilation from baseline up to Day 29 and setting days on mechanical ventilation to 29).

Treatment comparison will be based on analysis of covariance (ANCOVA) model including treatment as a factor, and study site, remdesivir use (No/Yes), dexamethasone use (No/Yes) and WHO Ordinal Scale for Clinical Improvement at baseline as covariates. Treatment difference, standard error, 95% confidence interval and p-value will be presented.

Example SAS codes for the analysis are as follows:

#### 6.12.2.5 All-cause mortality at Day 15, Day 22, and Day 29

The number and percentage for all-cause mortality will be summarized by treatment group and visit.

These endpoints will be analyzed using the same methodology as for the primary endpoint.

Responders are subjects who are alive at the time of the visit.

Non-responders are subjects who died before the visit.

Separate analysis will be performed for each visit.

QMD Ref: Worldwide-TMP-ST-005-7.0 Effective: 12Aug2019	Governing QMD: Worldwide-SOP-ST-001	
Confidentiality Statement		
This document is the property of Worldwide Clinical Trials Inc. and may not be duplicated, copied, altered or removed from company without		
prior approval from Worldwide Quality Assurance or in compliance with Worldwide Standard Operating Procedures		

Worldwide Clinical Trials Controlled Quality Management Document		
WORLDWIDE CLINICAL TRIALS	Sponsor:	Veru Inc.
	Protocol Number:	V0211901
STATISTICAL ANALYSIS PLAN. PHASE 2-3-4		

Responder rates and differences between treatment groups in responder rates will be calculated as sensitivity analysis using the same methodology as for the primary endpoint.

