# 6.12.2.6 Proportion of subjects alive and free of respiratory failure at Day 15, and Day 22

These endpoints will be analyzed using the same methodology as for the primary endpoint.

Separate analysis will be performed for each visit.

This will be the same analysis as for primary endpoint but just repeated for days 15 and 22.

# 6.12.2.7 Proportion of subjects alive and discharged from the ICU at Day 15, Day 22, and Day 29

The percentage of subjects alive and discharged from the ICU through Day 15, Day 22 and Day 29 (inclusive) will be summarized.

This analysis will compare the percentage of subjects that are alive and discharged from the ICU (responder) at Day 15, Day 22, and Day 29.

Responders are subjects who are alive and have been discharged from the hospital or not in the ICU at the time of the visit.

Non-responders are subjects who died before the visit or are in the ICU at the time of the visit.

This endpoint will be analyzed using the same methodology as for the primary endpoint.

Separate analysis will be performed for each visit.

# 6.12.2.8 Proportion of subjects alive and discharged from hospital at Day 15, Day 22, and Day 29

The percentage of subjects alive and discharged from the hospital through Day 15, Day 22 and Day 29 (inclusive) will be summarized.

This analysis will compare the percentage of subjects that are alive and discharged from the hospital (responder) at Day 15, Day 22, and Day 29.

Responders are subjects who are alive and have been discharged from the hospital at the time of the visit.

Non-responders are subjects who died before the visit or are in the hospital at the time of the visit.

This endpoint will be analyzed using the same methodology as for the primary endpoint.

QMD Ref: Worldwide-TMP-ST-005-7.0 Effective: 12Aug2019	Governing QMD: Worldwide-SOP-ST-001	
Confidentiality Statement		
This document is the property of Worldwide Clinical Trials Inc. and may not be duplicated, copied, altered or removed from company without prior approval from Worldwide Quality Assurance or in compliance with Worldwide Standard Operating Procedures.		

#### 

Separate analysis will be performed for each visit.

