#### 6.12.2.9 Days in ICU

'Days in ICU' will be summarized using descriptive statistics (n, mean, standard deviation, median, minimum and maximum) by treatment group.

'Days in ICU' will be the number of days in ICU up to Day 29. If subject dies early in the study and is in the ICU at the time of the death then it is assumed that subject was in the ICU up to Day 29.

'Days in ICU' will be analyzed using the same methodology as for 'Days in mechanical ventilation' and the same sensitivity analysis will be performed.

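### The 'discharged from the ICU' endpoint credits patients who were never in the ICU, and both ICU models adjust only partly for where patients started

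*Protocol*

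**What the plan says.** Protocol 5.3.2 lists the endpoint "Proportion of patients alive and discharged from the ICU at Day 15" and does not say how a patient who never entered the ICU counts. SAP 6.12.2.7 settles it: "Responders are subjects who are alive and have been discharged from the hospital or not in the ICU at the time of the visit". The complement is "Non-responders are subjects who died before the visit or are in the ICU at the time of the visit". Neither rule requires a previous ICU stay.

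Days in ICU (SAP 6.12.2.9) "will be the number of days in ICU up to Day 29", with ICU time extended to Day 29 for a subject who dies there. A subject never admitted scores zero by implication. The endpoint "will be analyzed using the same methodology as for 'Days in mechanical ventilation' and the same sensitivity analysis will be performed".

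The ICU proportion inherits the primary logistic model of SAP 6.12.1, and days in ICU inherits the ANCOVA of SAP 6.12.2.4. The ANCOVA terms are "treatment as a factor, and study site, remdesivir use (No/Yes), dexamethasone use (No/Yes) and WHO Ordinal Scale for Clinical Improvement at baseline as covariates", and the logistic model has the same set. The Protocol models (9.3.1, 9.4.1.4) have only site and baseline WHO score beside treatment. None has ICU status at entry.

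**The concern.** There are two separate issues.

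**Label.** A rate reported as discharge from the ICU mixes patients who left the ICU with patients who never went there. A reader cannot tell how much of it reflects recovery from intensive care.

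**Adjustment.** A patient in the ICU on Day 1 starts as a non-responder and accrues ICU days at once; a ward patient starts as a responder with zero days. Starting location is thus the outcome's own baseline value. For the ventilation endpoints the WHO score carries that value, since level 6 is intubation. For the ICU endpoints it does not: the scale grades respiratory and organ support, not location, and a patient at level 4 or 5 could be on a ward or in an ICU. With about 20 per arm and no stratification described, the arms may well differ in starting location, and the planned models remove only part of the effect. ICU status is also absent from the Day 1 assessments (Protocol 8.3) and the baseline variables in SAP 6.6. The content of the Baseline Condition table (14.1.2.3) is not specified, so an imbalance may go unseen.

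**Working it through.** The plan has no figure to reproduce: both documents state that no power calculation was done, and neither gives an ICU rate.

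**1. Responder rule.** Take a ward patient on nasal oxygen who never enters the ICU and is alive at Day 15. The patient is not in the ICU, so is a responder, and meets neither non-responder condition. Days in ICU is 0, which is a correct count. The label problem therefore concerns the proportion only.

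**2. Mixed starting location.** Room-air SpO2 of 94% or less meets the oxygenation criterion (Protocol 6.2.1). WHO 5, and WHO 6 for less than five days, may also enter (6.2.2). Nothing fixes location.

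**3. Chance of imbalance.** The input is 20 per arm (Protocol 6.1); the ICU share p is assumed. With X1 and X0 independent Binomial(20, p), compute P(|X1 - X0| >= 4), a difference of at least 20 points:

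| p | 15% | 20% | 30% | 40% | 50% |
|---|---|---|---|---|---|
| Probability | 12% | 16% | 23% | 26% | 27% |

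These are raw differences, before any WHO adjustment.

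**4. What the WHO score leaves.** Simulation with no treatment effect, 20 per arm. All rates are assumptions:
- Baseline WHO 3/4/5/6: 5/55/25/15%.
- ICU at entry by WHO 3/4/5/6: strong link 0/5/85/100%, moderate 5/20/60/100%, weak 20/30/45/90%.
- ICU days: gamma with shape 1.5, capped at 29. The scale is 11 if in the ICU at WHO 6, and 6.5 if in the ICU at a lower score. Of those starting outside, 15% are admitted later (scale 6).
- Response: 92% outside the ICU at entry, 65% inside, 40% inside at WHO 6.
- Site and the two drug-use terms omitted; 6,000 runs for days, 3,000 for the proportion (lightly penalised logistic, standardised risk difference).

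Mean shift when one arm has an ICU share at entry at least 20 points higher:

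| | Strong | Moderate | Weak |
|---|---|---|---|
| Days, unadjusted | 2.54 | 2.53 | 2.52 |
| Days, WHO in model | 0.70 | 1.34 | 1.92 |
| Days, WHO + ICU status | 0.01 | -0.06 | 0.02 |
| Proportion, unadjusted (points) | -9.5 | -8.6 | -8.9 |
| Proportion, WHO in model | -2.0 | -4.1 | -6.0 |
| Proportion, WHO + ICU status | -0.4 | -0.2 | -0.1 |

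Share of the shift remaining after WHO adjustment: for days, 0.70/2.54 = 28%, 1.34/2.53 = 53%, 1.92/2.52 = 76%. For the proportion, 2.0/9.5 = 21%, 4.1/8.6 = 48%, 6.0/8.9 = 67%.

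**5. Precision.** Variance with WHO alone, divided by variance with WHO plus ICU status:
- Days: 1.08, 1.27, 1.38. As a reduction, 1 - 1/1.08 = 7%, 1 - 1/1.27 = 21%, 1 - 1/1.38 = 28%.
- Proportion: (0.116/0.116)^2 = 1.00, (0.120/0.117)^2 = 1.05, (0.125/0.119)^2 = 1.10. As a reduction, 0%, 5% and 9%.

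**6. Sensitivity to the assumptions.** With a WHO mix of 10/50/25/15%, ICU shares of 5-15% at WHO 4, 50-90% at WHO 5 and 100% at WHO 6, and 15-30% of ward patients admitted later, the reduction for days was 10-40%. One case took the standard error from 2.05 to 1.60 days: 1 - (1.60/2.05)^2 = 39%. A further run with that WHO mix gave 13-25%, and a shift of 0.8-1.5 days under imbalance. With site in the model, the reduction was 8-11% and the shift 0.7-1.2 days.

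**The case against.** A reader might infer that an entry imbalance goes straight into the ICU results. The documents do not support that for the modelled analyses: the baseline WHO score is in every one and tracks much of the severity behind ICU placement. The inference holds only for the unadjusted summaries (tables 14.2.6.1, 14.2.8.1 and 14.2.8.3). The 12-27% likewise overstates the risk for the models. With the WHO mix in step 6, the chance of a gap of at least 20 points that remains after WHO adjustment was 3%, 6% and 9.5% for strong, moderate and weak links, against 24-26% raw. Site is also in the planned model and may absorb differences between hospitals in ICU use.

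A reader might also infer bias. Under randomisation the imbalance is chance error; the comparison is valid, and the responder rule covers every randomised subject. Nor may one say that if 60-80% start and stay outside the ICU the rate must be at least that high: a ward patient who dies before the visit is a non-responder.

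Finally, SAP 6.12.4 treats secondary endpoints as descriptive, the trial is an unpowered proof of concept, and the logistic model is already crowded for about 40 subjects.

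All of this limits the size and priority. It does not remove the misnomer or the missing baseline term. The results will still carry confidence intervals and p-values, and all four days-in-ICU tables (14.2.8.1-14.2.8.4) are marked for the preliminary analysis.

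**Conclusion.** The point holds in a limited form; its priority is minor. The name of the proportion endpoint does not match its rule, because living patients never admitted are responders. Neither ICU model includes ICU status at entry, and the WHO score replaces it only in part. Under the assumed ICU shares and outcome rates, an entry imbalance of at least 20 points leaves roughly 0.7-1.9 days after WHO adjustment. Adding the term reduces variance by roughly 7-40% for days in ICU and 0-10% for the proportion. The case for a covariate thus rests mainly on days in ICU; for the proportion it is chiefly labelling and display. The documents supply no ICU shares, so these sizes are indicative.

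**What to change.** - **SAP 6.12.2.9:** add ICU status at entry (yes/no, last known status up to Day 1) to the ANCOVA for days in ICU. The ICU data needed to count days should supply it, though the documents describe no specific field.
- **SAP 6.12.2.7:** keep the responder rule, state that never-admitted subjects are responders, and rename the endpoint 'alive and not in the ICU'. Show table 14.2.6.1 by ICU status at entry, and give a Mantel-Haenszel rate difference stratified by it, rather than a further logistic term.
- **Baseline tables:** tabulate ICU status at entry by arm.

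The cost is SAP wording, one ANCOVA parameter and a few table columns. Day 1 status may not be certain to precede the first dose, a difficulty that SAP 6.12.2.1 already acknowledges for the WHO score. A sensitivity analysis on screening status, as planned there, is suitable if that status is available.
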